3. Data are not needed to be entered in the electronic case report form (eCRF) again if already collected and entered in eCRF for a previous screening for this study within 30 days before current screening.
4. Reversibility testing ([Appendix 10.3](#)) can be omitted if patient took part in one of the SRD groups before.
5. Vital signs must be completed prior to bodyplethysmography.
6. Letters A, B and C describe different sets of safety laboratory examinations (see [Section 5.2.4](#)).
7. Urine drug screening will be performed at screening and prior to dosing on Day 1 of visit 3. A breath alcohol test will be performed prior to BI 894416 or placebo administration in Visit 3, and may be repeated at any time during the study at the discretion of an investigator or designee.
8. [REDACTED]
9. PK samplings and ECGs should be done in direct sequence for matching reasons. Please refer to Flow Chart “[MRD part – Time schedule](#)”;
10. This sample is optional. A separate consent is required. In case a patient takes part in both a SRD and a MRD dose group only one pharmacogenomic sample is to be taken.
11. At Day 1 the following procedures must be completed prior to BI 894416 or placebo administration: Safety laboratory, neurological examination, Vital signs, ECG, PD and PK samplings. The respective procedures are to be performed and completed within 3 h prior to BI 894416 or placebo administration. Allocation to treatment at Visit 3 could be performed at any time following enrolment but had to be completed prior to BI 894416 or placebo administration.
12. BI 894416 or placebo administration at Day 1 and Day 9 once daily in the morning (qd) and at Day 2 to Day 8 three times daily at an interval of 8 hours (tid).
13. PK samples for plasma level determination of BI 894416 [REDACTED] are to be taken at the time points as outlined in Flow Chart “MRD part – Time schedule”; [Section 5.3.2.2](#) and in [Appendix 10.2](#). [REDACTED], Section 5.3.2.2 and in Appendix 10.2. Sampling times and periods may be adapted based on information obtained during the trial (e.g. preliminary PK [REDACTED] data) including addition of samples and visits as long as the total blood volume taken does not exceed 500 mL per patient.
14. [REDACTED]

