15. PK urine samplings for determination of BI 894416 amount eliminated in urine are to be taken at following time intervals: A blank urine sample is to be obtained within 3 hours prior to administration of trial medication. [REDACTED] Other urine samples are to be collected over the stated post-dose intervals 0-4, 4-8, 8-12 and 12-24h after BI 894416 or placebo administration on Day 1 and Day 9 only.
16. AEs and concomitant therapies will be recorded throughout the trial, but will be specifically asked at time points indicated in the Flow Chart “MRD part – Time schedule”.
17. Safety laboratory to be taken and to be medically evaluated within 3 days (within 76 hours) prior to administration of BI 894416; this ambulatory visit for safety laboratory and questioning for AEs and concomitant therapies can be omitted if the screening examination is performed on Day -3 or if lab sample can be taken on Day -1 and the lab results can be medically evaluated before BI 894416 or placebo administration at Day 1, [Tables 5.2.4: 1](#) and [5.2.4: 2](#).
18. Three triplicate ECGs are recorded within approximately one hour. The recordings should be separated by at least 15 minutes (refer to Flow Chart “MRD part – Time schedule” and to [Section 5.2.5.1](#));
19. Triplicate ECG (refer to Flow Chart “MRD part – Time schedule” and to Section 5.2.5.1);
20. Oral with 240 mL of water after an overnight fast of at least 10 h; (please also refer to [Section 4.2.2.2](#))
21. Oral with 240 mL of water

Proprietary confidential information © 2020 Boehringer Ingelheim International GmbH or one or more of its affiliated companies

- ^{22.} Physical examination includes an echocardiography (stress) test in the screening period in patients aged 45 and older. Assessment can be omitted if patient took part in one of the SRD groups before.
- ^{23.} SARS-CoV-2 PCR Test will be done at Visit 2 only. Result must be available prior to randomization. Result must be available prior to randomization. If Visit 2 is omitted (see [footnote 17](#)), the test must be performed on day -3 to -1.

MRD PART / TIME SCHEDULE

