1.4.2 Procedure-related risks

The use of an indwelling venous catheter for the purpose of blood sampling may be accompanied by mild bruising and also, in rare cases, by transient inflammation of the wall of the vein. In addition, in rare cases a nerve might be injured while inserting the venous catheter, potentially resulting in paresthesia, reduced sensibility, and/or pain for an indefinite period. The same risks apply to venipuncture for blood sampling.

ECG electrodes may cause local and typically transient skin reactions.

The total volume of blood (including volume needed for the Platelet Function Assay) withdrawn during the entire study per patient will not exceed the volume of a normal blood donation (500 mL). No health-related risk to patients is expected from this blood withdrawal.

Patients will be followed up until 14 days after the last treatment.

ther study

Proprietary confidential information © 2020 Boehringer Ingelheim International GmbH or one or more of its affiliated companies

procedures such as spirometry, bodyplethysmography, [REDACTED] and blood pressure measurement are not expected to cause any adverse events.

An echocardiography (stress) test will only be performed in patients over 45 years of age. Complications may include arrhythmias, hypotension, acute coronary syndrome, heart failure, light-headedness, exercise-related injury, body aches and fatigue. Acute coronary syndrome is rare. Complications are rare, especially with patients having no pre-existent reason for testing or cardiac history, both of which would have been excluded in any case.

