- A documented Safety Review takes place prior to next dose level, both for the MRD and for the SRD part. The next dose level in either part is only permitted if there are no safety concerns precluding the next dose level in the SRD and MRD part and if none of the pre-specified stopping criteria are met. The minimum time interval between dosing of the first patient of an SRD dose group (dose group N) and dosing of the first patient of the subsequent SRD dose group (dose group N+1) is at least 12 days. The minimum time interval between first dosing of the first patient of an MRD dose group (dose group N) and first dosing of the first patient of the subsequent MRD dose group (dose group N+1) is at least 21 days. For details see [Section 3.1](#) and [Appendix 10.1](#).
- Patients with relevant neurological disorder in the medical history are excluded from trial participation (see [Section 3.3.3](#)). Neurological examinations will be performed at screening, baseline and pre-defined time points during treatment (see [Flow Charts](#) and [Section 5.2.2](#)). Additional neurological examinations may be performed as necessary upon investigator judgment. If necessary, patients may be sent for further evaluation and treatment to a local neurologist.
- Patients 45 years of age and older will be screened for potential cardiovascular issues at screening by an echocardiography and echocardiography stress test. These patients would be excluded from the trial. The procedure is implemented because of the early nature of this program and not because of any specific cardiac risk of this compound.
- Safety laboratory examinations will be performed at pre-defined time points before and for at least two weeks after the last trial medication administration. These examinations include extensive standard safety laboratory examinations. In addition, immune monitoring (including white blood cell count, differential blood count, lymphocyte differentiation and immunoglobulins) will be included as detailed in [Flow Charts](#) (time points) and [Section 5.2.4](#) (test details).
- A thorough ECG and heart rate monitoring including continuous ECG monitoring for 4 h post dose (SRD part only) and in addition frequent 12-lead ECG and vital signs measurements at time points as described in the [Flow Chart](#) are planned.

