3.3.2 Inclusion criteria

Patients will only be included into the trial, if they meet the following criteria:

1. Signed and dated written informed consent in accordance with ICH-GCP and local legislation prior to admission to the trial. Medication washout and medication restrictions according to protocol are allowed only after informed consent is obtained.
2. Male patients aged at least 18 years but not more than 55 years at the time of informed consent.
3. Men able to father a child must be ready and able to use highly effective methods of birth control per ICH M3 (R2) that result in a low failure rate of less than 1% per year when used consistently and correctly. A list of contraception methods meeting these criteria is provided in the patient information.
4. Pre-bronchodilator clinic measured FEV₁ of $\geq 70\%$ of predicted normal at the screening visit (Visit 1). Calculations will be based on Global Lung Function Initiative (GLI) formula ([R15-0845](#)).
5. A diagnosis of asthma, diagnosed by a physician.
6. Patients should be non-smokers or ex-smokers who stopped smoking at least 12 weeks prior to screening and are expected to be able to not smoke for the duration of the study.
7. Patients must be able to perform all trial related procedures including pulmonary function tests, nasal brushings.
8. BMI of 18.5 to 32 kg/m² (incl.)
9. For MRD part: Patients are allowed to be on stable inhaled low dose corticosteroid (please refer to GINA guidelines) for at least 4 weeks prior to screening.

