3.3.3 Exclusion criteria

Patients will not be allowed to participate if any of the following general criteria apply:

1. Any finding in the medical examination (including BP, PR, echocardiography and echocardiography stress test or ECG and including the neurological examination) is deviating from normal and judged as clinically relevant by the investigator
2. Repeated measurement of systolic blood pressure outside the range of 90 to 140 mmHg, diastolic blood pressure outside the range of 50 to 90 mmHg, or pulse rate outside the range of 50 to 90 bpm
3. Any laboratory value outside the reference range that the investigator considers to be of clinical relevance

Proprietary confidential information © 2020 Boehringer Ingelheim International GmbH or one or more of its affiliated companies

4. Any evidence of a concomitant disease judged as clinically relevant by the investigator
5. Gastrointestinal, hepatic, renal, respiratory, cardiovascular (stress), metabolic, immunological or hormonal disorders
6. Relevant abnormality on stress echocardiography for those 45 of age and older at screening.
7. Cholecystectomy and/or surgery of the gastrointestinal tract that could interfere with the pharmacokinetics of the trial medication (except appendectomy and simple hernia repair)
8. Diseases of the central nervous system (including but not limited to any kind of seizures or stroke), and other relevant neurological or psychiatric disorders
9. History of relevant orthostatic hypotension, fainting spells, or blackouts
10. Chronic or relevant acute infections
11. History of relevant allergy or hypersensitivity (including allergy to the trial medication or its excipients)
12. Use of drugs within 30 days prior to administration of trial medication that might reasonably influence the results of the trial (incl. QT/QTc interval prolongation)

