13. Participation in another trial where an investigational drug other than BI 894416 has been administered within 60 days or 5 half-lives (whichever is greater) prior to planned administration of trial medication, or current participation in another trial involving administration of investigational drug. In case of planned participation in the MRD part in this trial the previous participation in one dose group of the SRD part is allowed if BI 894416 has been administered more than 21 days prior to planned administration of BI 894416 in the MRD part. (Participation in an SRD dose group after the patient has participated in the MRD part is not allowed.)
14. Alcohol abuse (consumption of more than 24 g per day) (please refer to [Appendix 10.5](#))
15. Drug abuse or positive drug screening
16. Blood donation of more than 100 mL within 30 days prior to administration of trial medication or intended donation during the trial
17. Intention to perform excessive physical activities within one week prior to administration of trial medication or during the trial
18. Inability to comply with dietary regimen of trial site
19. A marked baseline prolongation of QT/QTc interval (such as QTc intervals that are repeatedly greater than 450 ms) or any other relevant ECG finding at screening
20. A history of additional risk factors for Torsades de Pointes (such as heart failure, hypokalemia, or family history of Long QT Syndrome)
21. Patient unable or unwilling to comply with study requirements, or has a condition that would not allow safe participation in the study
22. History of relevant neurological disorder affecting the peripheral or central nervous system (this includes, but is not limited to: stroke, epilepsy, inflammatory or atrophic diseases affecting the nervous system, cluster headache or any cancer of the nervous system)*
23. History of immunological disease except allergy not relevant to the trial (such as mild hayfever or dust mite allergy) and except asthma in childhood or adolescence

Proprietary confidential information © 2020 Boehringer Ingelheim International GmbH or one or more of its affiliated companies

24. History of cancer (other than successfully treated basal cell carcinoma)
25. Use of any drug that could reasonably inhibit platelet aggregation or coagulation (e.g. acetylsalicylic acid) within 10 days prior to administration of trial medication, or planned use during the trial or within 7 days after last dose of trial medication.

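### The MRD flow chart waives the stress echocardiogram on SRD participation alone, so a man who turns 45 between the parts may have it omitted although no earlier result exists, contrary to exclusion criterion 6

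*Protocol*

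**What the plan says.** Both parts require the test by age. SRD overview footnote 20, SRD time-schedule footnote 17, MRD overview footnote 22 and MRD time-schedule footnote 21 all state: "Physical examination includes an echocardiography (stress) test in the screening period in patients aged 45 and older". The two MRD footnotes then add: "Assessment can be omitted if patient took part in one of the SRD groups before".

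Exclusion criterion 6 (protocol 3.3.3) reads: "Relevant abnormality on stress echocardiography for those 45 of age and older at screening". Section 1.4.3.3 lists the test as a safety measure: "Patients 45 years of age and older will be screened for potential cardiovascular issues at screening by an echocardiography and echocardiography stress test". Section 5.2.1 puts it in the screening examination from the same age. Neither section mentions a waiver.

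A patient may take part once in each part, SRD first. Under exclusion criterion 13, "previous participation in one dose group of the SRD part is allowed if BI 894416 has been administered more than 21 days prior" to the MRD dose. That sets a minimum gap and no maximum. Inclusion criterion 2 admits "Male patients aged at least 18 years but not more than 55 years at the time of informed consent", so men of 44 and of 45 are both eligible.

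Section 8.3.1 requires source evidence, before a patient is allocated to treatment, that no exclusion criterion is met. It adds that missing records, including results of protocol-specific tests, do not make a patient eligible.

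Section 1.4.2 words the age limit differently: "An echocardiography (stress) test will only be performed in patients over 45 years of age".

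**The concern.** A waiver of this kind is sound if everyone it covers already has the result. Reversibility testing shows the contrast. MRD overview footnote 4 waives it in nearly the same terms, and that works because every SRD patient has the test at screening. The stress echocardiogram depends on age, so SRD participation does not guarantee that one was done.

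At stake is whether an exclusion criterion can be judged for every patient it covers. For a man who reaches 45 between the parts, the flow chart says the test may be left out, while criterion 6 and sections 1.4.3.3, 5.2.1 and 8.3.1 presuppose a result. Sites tend to work from the flow chart, so the contradiction could lead to enrolment with criterion 6 unassessed.

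The 1.4.2 wording adds a smaller inconsistency. Read literally, it leaves out a man aged exactly 45, whom the other sections include.

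**Working it through.** The plan gives no figure to reproduce on this point. The check compares the passages and then estimates how often the case could arise.

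**Passages side by side, for a man aged 44 at SRD screening and 45 at MRD screening**

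| Step | Source | Result |
|---|---|---|
| SRD screening, age 44 | SRD footnotes 20 and 17 (from 45) | Test not required; no result |
| Move to the MRD part | Exclusion criterion 13 | Allowed if the SRD dose was more than 21 days before |
| MRD screening, age 45 | Exclusion criterion 6 | Criterion applies; a result is needed |
| MRD screening, age 45 | 1.4.3.3 and 5.2.1 | Test to be done; no waiver |
| MRD screening, age 45 | MRD footnotes 22 and 21 | Test may be omitted because he was in the SRD part |
| Before allocation | 8.3.1 | No record, so not shown to be eligible |

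The last four rows cannot all be followed if the waiver is used.

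**How often it could happen**

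Inputs:
- Ages 18 to 55 inclusive give 38 one-year bands (inclusion criterion 2).
- The planned number of SRD patients is 30. SAP 6.1 states that the SRD part stopped after 170 mg and that 175 mg and 225 mg were not performed, which leaves three groups of 10.
- The gap is more than 21 days. A generous upper end is 16 months, from Amendment 1 (18 June 2019) to protocol version 6.0 (14 October 2020). The documents give no dosing dates, so this is an assumption.
- The documents give neither an age distribution nor the number who went on to the MRD part. Ages are taken as evenly spread and all 30 as re-entering, both as assumptions.

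Formula: share turning 45 in the gap = (gap in years) / 38; expected number = 30 × share.

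| Gap | Share | Expected of 30 |
|---|---|---|
| 22 days (0.060 y) | 0.16% | 0.05 |
| 365 days (0.999 y) | 2.6% | 0.8 |
| 16 months (1.333 y) | 3.5% | 1.05 |

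The 16-month gap cannot apply to all 30. Preliminary PK results for 10, 25 and 50 mg t.i.d. were already in the protocol with Amendment 4 (15 May 2020), so patients in those groups had gaps of at most about 11 months from June 2019: (11/12)/38 = 2.4%. Only the 10 patients planned for 60 mg t.i.d. came later. That gives 10 × 3.5% + 20 × 2.4% = 0.35 + 0.48 = about 0.8.

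**The case against.** The best reply is that the protocol closes the gap elsewhere. Section 8.3.1 bars allocation when the record for a criterion is missing, the waiver is permissive, and its natural sense is that a test already done need not be repeated. An investigator applying 8.3.1 strictly would still do the test. This softens the consequence but does not cure the text. Section 8.3.1 conflicts with the footnote without amending it, and the footnote nowhere says that a test must have been done.

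A reader might infer that such a man receives no cardiac screening. The documents do not support that. MRD screening still includes physical examination, vital signs and a 12-lead ECG with a rhythm strip of at least 15 minutes. Exclusion criteria 1, 2, 5, 19 and 20 cover clinical and ECG findings, blood pressure and pulse, cardiovascular disorders, QTc prolongation and risk factors for Torsades de Pointes at any age. Triplicate ECGs follow on Day -1. One component is missing. Section 1.4.3.3 also attributes the test to the early stage of the programme and not to a specific cardiac risk of the compound.

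A reader might also want a maximum age for an earlier result in men who were tested in the SRD part. No passage sets one. The 30-day limit in MRD overview footnote 3 ("for a previous screening for this study within 30 days before current screening") governs re-entry of data in the eCRF and cannot be borrowed for this purpose.

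Finally, the age limits are not three competing thresholds. Section 1.4 refers to patients beyond 44, which is the same as 45 and older. Only 1.4.2 differs, and it is risk narrative, not an eligibility rule.

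**Conclusion.** The contradiction is real and narrow. As written, the MRD footnotes let the stress echocardiogram be omitted for a patient who is subject to exclusion criterion 6 and has never had the test. The expected number is about one or fewer, assuming that all of about 30 planned SRD patients re-entered, ages were evenly spread over 18 to 55, and gaps reached up to 16 months. With fewer re-entrants or shorter gaps it falls towards zero. A reader who counts SRD patients from the protocol's planned 40 or 50 would overstate it, because the SAP reports that two SRD groups were not performed.

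The point concerns eligibility and the consistency of a safety measure. It does not touch the endpoints, analysis sets or any estimate. It merits correction because a stated rule conflicts with an exclusion criterion and the correction is small.

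**What to change.** Reconcile MRD overview footnote 22 and MRD time-schedule footnote 21 with exclusion criterion 6 and sections 1.4.3.3, 5.2.1 and 8.3.1. The waiver should depend on a stress echocardiogram documented for that patient at SRD screening, not on SRD participation alone. Separately, reconcile the age wording in 1.4.2 with that in the flow charts, 1.4.3.3, 3.3.3 and 5.2.1.

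The cost is two footnotes and one sentence, plus a test the protocol already requires in the very few re-entering men of 45 or older who have no SRD result. The SAP needs no change.

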Proprietary confidential information © 2020 Boehringer Ingelheim International GmbH or one or more of its affiliated companies

FAS	Full Analysis Set
FC	Flow Chart
[REDACTED]	[REDACTED]
[REDACTED]	[REDACTED]
[REDACTED]	[REDACTED]
FEV1	Forced Expiratory Volume (Pressure) in 1 second
[REDACTED]	[REDACTED]
FOB	Faecal occult blood
[REDACTED]	[REDACTED]
FVC	Forced (expiratory) Vital Capacity
GCP	Good Clinical Practice
gCV	Geometric coefficient of variation
GI	Gastro-intestinal
GINA	Global Initiative for Asthma
gMean	Geometric mean
HPC	Human Pharmacology Centre
HPLC-MS/MS	High performance liquid chromatography with tandem mass spectrometry
HR	Heart rate
IB	Investigator's Brochure
IEC	Independent Ethics Committee
iPD	Important protocol deviation
IRB	Institutional Review Board
IRT	Interactive Response Technology
ISF	Investigator Site File
i.v.	intravenous
[REDACTED]	[REDACTED]
[REDACTED]	[REDACTED]
LC-MS/MS	Liquid chromatography with tandem mass spectrometry
LLOQ	Lower limit of quantification
LoEE	List of Essential Element
MDA	Methylenedioxymphetamine
MDMA	Methylenedioxymethamphetamine
MedDRA	Medical Dictionary for Regulatory Activities
[REDACTED]	[REDACTED]
MRD	Multiple-rising dose
[REDACTED]	[REDACTED]

[REDACTED]	[REDACTED]
MST	Medical Sub Team
NOTEI	No toxic effect level
OPU	Operative Unit
[REDACTED]	[REDACTED]
PE	Polyethylene
PEF	Peak Expiratory Flow
PfOS	Powder for reconstitution of an oral solution
PFT	Pulmonary Function Test
PIB	Powder in the bottle
PK	Pharmacokinetic(s)
PKS	Pharmacokinetic set
p.o.	per os (oral)
PP	Polypropylene
ppb	Parts per billion
PR	Pulse rate
PTF	Peak-Trough Fluctuation
PTS	Peak-trough swing
q.d.	queaque die (once a day)
QT	Time between start of the Q-wave and the end of the T-wave in an electrocardiogram
QTc	QT interval corrected for heart rate using the method of Fridericia (QTcF) or Bazett (QTcB)
R	Reference treatment
[REDACTED]	[REDACTED]
[REDACTED]	[REDACTED]
Raw	Airway Resistance
REP	Residual Effect Period
RR	Respiratory rate
RV	Residual Volume
SAE	Serious Adverse Event
s.c.	subcutaneous
SCR	Screening
SMC	Safety Monitoring Committee

Proprietary confidential information © 2020 Boehringer Ingelheim International GmbH or one or more of its affiliated companies

SmPC	Summary of Product Characteristics
SOP	Standard Operating Procedure
SRD	Single-rising dose
ss	(at) steady state
SUSAR	Suspected unexpected serious adverse reaction
██████████	██████████
SYK	Spleen Tyrosine Kinase
T	Test product or treatment
██████████	██████████
██████████	██████████
██████████	██████████
██████████	██████████
██████████	██████████
TDMAP	Trial Data Management and Analysis Plan
t.i.d.	ter in die (3 times a day)
TMF	Trial Master File
TS	Treated set
TSAP	Trial Statistical Analysis Plan
ULN	Upper limit of normal
US PI	US Package Insert
██████████	██████████
██████████	██████████
██████████	██████████
██████████	██████████
WHO	World Health Organization
WOCBP	Woman of childbearing potential

